13.1.9.1. Time to Event Endpoints

For the time to event analyses, subjects who do not experience an event will be censored at the time of their last contact. Subjects with no data after randomization will be considered to have an event on Day 1 (first day of investigational product dosing).

For analyses of the percentage of subjects with an event, subjects with no data after randomization will be considered to have an event.

All time to event endpoints include only adjudicated events. Sensitivity analyses may consider all events regardless of adjudication. Events with discrepant adjudication will be analyzed using both results.

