13.1.3. Primary Efficacy Analysis

The primary efficacy endpoint will be the time to first occurrence of one of the following post-randomization:

- Death (all-cause)
- Liver transplant
- MELD score ≥ 15
- Hospitalization (as defined by a stay of 24 hours or greater) for new onset or recurrence of:
 - Variceal bleed
 - Hepatic encephalopathy (as defined by a West Haven score of ≥ 2)
 - Spontaneous bacterial peritonitis (confirmed by diagnostic paracentesis)
- Uncontrolled ascites (diuretic resistant ascites requiring therapeutic paracentesis at a frequency of at least twice in a month).

The primary efficacy analysis will compare OCA to placebo with respect to the primary efficacy endpoint using the ITT population. Only adjudicated events will be included in analyses. The 2 treatment groups will be compared using the log rank test stratified by the randomization stratification factor. Kaplan-Meier (KM) estimates of the distribution of the time-to-event will be tabulated and graphed by treatment group. The tabulation will include the KM estimate of the medians and corresponding 95% confidence intervals (CIs), if the medians can be estimated. The number and percent of subjects censored and with events will be presented. The hazard ratio and 95% CI will be determined based on a Cox regression model stratified by randomization strata to estimate the magnitude of the effect. The same analyses for primary efficacy endpoints will be performed for PP population as a sensitivity analysis.

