13.1.4. Key Secondary Efficacy Analyses

The key secondary efficacy endpoints will compare OCA to placebo on the following:

- Time to first occurrence of MELD score ≥ 15

- Time to liver transplant or death (all-cause)
- Change from Baseline in total bilirubin at end of study
- Change from Baseline in ALP at end of study

The key secondary efficacy analyses will compare OCA to placebo in the ITT population with respect to the key secondary efficacy endpoints. Only adjudicated events will be included in time-to-event analyses. The comparison (hypothesis testing) will be conducted as specified in [Section 13.1.10](#) in a sequential closed testing gate-keeping procedure, provided that the primary efficacy endpoint comparison is statistically significant in favor of the OCA treatment group. If the primary comparison is not statistically significant then comparison of the secondary endpoints will be considered as descriptive and exploratory. This procedure controls the study-wise type I error.

The 2 treatment groups will be compared using the same methodology as specified for the primary efficacy analysis ([Section 13.1.3](#)). The same analyses for key secondary efficacy endpoints will be performed for PP population as a sensitivity analysis.

Analyses of change from Baseline to end of study in ALP and total bilirubin will be compared between treatment groups using analysis of covariance (ANCOVA) with change from Baseline as the dependent variable including treatment group and randomization stratification factor as fixed effects and the Baseline values as a covariate. The same analysis will be carried out using percentage change from Baseline as the dependent variable.

Descriptive statistics of the laboratory values will be summarized by treatment group. The results, change from Baseline, and percentage change from Baseline values as well as estimates of least-square means, standard errors, and 95% CIs will be presented by treatment group. Estimates of the mean difference between treatment groups, the standard error of the difference, and 95% CI of the difference will be presented.

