13.1.5. Additional Secondary Efficacy Analyses

The following time-to-event secondary efficacy analyses will compare OCA versus placebo using the ITT population:

- Time to each component of the primary efficacy endpoint (except MELD score ≥ 15 which is captured above)
- Time to development of varix/varices
- Progression to cirrhosis
- Time to occurrence of HCC
- Time to liver-related death
- Time to liver-related death or liver transplant
- Time to liver-related death, liver transplant, or MELD score ≥ 15

The same analysis methodology as used for the primary efficacy analysis will be used for these secondary efficacy analyses. Similar endpoints, where available, will be analyzed to compare OCA to historical controls as described below in [Section 13.1.8](#).

Analyses of changes in liver biochemistry (GGT, ALT, AST, conjugated bilirubin, albumin, and INR) will be summarized and analyzed using the same methodology as specified in [Section 13.1.4](#) for the key secondary analyses of change in ALP and total bilirubin.

Progression to cirrhosis will be assessed in the subset of subjects considered noncirrhotic at Baseline using available medical history, clinical, and laboratory assessments as well as baseline TE, where available. Specifically, subjects with no clinical, laboratory, or radiological evidence of cirrhosis at baseline and/or a TE liver stiffness of <16.9 kPa ([Corpechot 2012](#)) will be considered noncirrhotic (See [Section 7.5.4](#)). Progression to cirrhosis will be assessed by the development of clinical, laboratory, or radiological evidence of cirrhosis and/or when liver stiffness increases to ≥ 16.9 kPa during the study in which case histological progression to cirrhosis should be confirmed by biopsy unless not medically indicated. Using this definition for progression to cirrhosis, the percentage of noncirrhotic subjects progressing to cirrhosis during the treatment period will be summarized by treatment group and compared using a Cochran-Mantel-Haenszel test stratified by the randomization stratification factor.

For those subjects enrolled in the biopsy substudy (defined in Addendum 2) progression to cirrhosis identified by the above criteria and improvement in fibrosis/cirrhosis will be confirmed by paired biopsy. Analyses for the histological assessment conducted as part of the biopsy substudy are defined in Addendum 2).

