KM estimates of the distribution of the time-to-event will be tabulated and graphed by treatment group. The tabulation will include the KM estimate of the medians and corresponding 95% CIs if the medians can be estimated. The number and percent of subjects censored and with events will be presented. The hazard ratio and 95% CI will be determined based on a Cox regression model stratified by randomization strata to estimate the magnitude of the effect.

Sensitivity analyses will be conducted limiting to the separate individual historical control databases, ie, UK-PBC Group and Global PBC Study Group. To evaluate the robustness of the propensity score estimations, additional algorithms and factors may be considered.

Although the study is designed as a placebo-controlled study, the DMC may recommend changes to study conduct based on the pre-specified interim analyses (see [Section 13.1.12](#)), including the potential use of a revised primary efficacy analysis. This analysis would compare all subjects in the OCA population, to all control subjects (randomized placebo and historical controls) on time to liver transplant or death (all-cause), using similar statistical methodology as specified above.

Notably, the planned primary analysis would not be revised without prior agreement with regulatory authorities.

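### For endpoints that exclude all-cause death, censoring at death plus Kaplan-Meier overstates the event probability patients face, modestly; the tests and the sample size are unaffected

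*Protocol*

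**What the plan says.** Protocol Section 13.1.9.1 gives the general censoring rule: "For the time to event analyses, subjects who do not experience an event will be censored at the time of their last contact". It does not distinguish death from loss to follow-up.

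Section 13.1.3 defines the primary method as a stratified log-rank test, a stratified Cox model and Kaplan-Meier reporting: "Kaplan-Meier (KM) estimates of the distribution of the time-to-event will be tabulated and graphed by treatment group". Two sections carry that method further:

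- Section 13.1.4, key secondary endpoints: "The 2 treatment groups will be compared using the same methodology as specified for the primary efficacy analysis". The first in the hierarchy is "Time to first occurrence of MELD score" of 15 or more.
- Section 13.1.5, additional secondary endpoints: "The same analysis methodology as used for the primary efficacy analysis will be used for these secondary efficacy analyses". The list includes "Time to each component of the primary efficacy endpoint", development of varices, "Time to occurrence of HCC", liver-related death, and liver-related death combined with transplant, with or without MELD of 15 or more.

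Section 13.1.8 repeats the instruction for the historical-control comparison: "KM estimates of the distribution of the time-to-event will be tabulated and graphed by treatment group". The outcomes there include transplant alone, liver-related death, and the two combined. The protocol does not mention competing risks or cumulative incidence.

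**The concern.** The primary composite and the endpoint of transplant or all-cause death both count every death as an event, so Kaplan-Meier is right for them. The other endpoints can be made impossible by death. A subject who dies without HCC can no longer develop it, and a subject who dies of a non-liver cause can no longer die of liver disease. Transplant can also remove the possibility of some later events.

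Censoring such a subject at last contact treats them as still able to have the event later. One minus Kaplan-Meier then describes a hypothetical setting without the competing deaths. At stake are the tabulated and graphed component probabilities, any medians read from them, and the absolute differences between arms that a reader would take from the curves.

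**Working it through.** **Design inputs (Section 13.1.2).** Placebo event-free proportion 0.6 at 8 years, hazard ratio 0.60, 1:1 allocation, two-sided 5%, 80% power, 4 years of accrual plus 6 of follow-up, 10% dropout, 127 events, about 428 subjects. Section 13.1.12 adds looks at 64 and 96 events with Lan-DeMets O'Brien-Fleming boundaries.

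**The plan's own figures reproduce.**
- Events, fixed design: Schoenfeld 4(1.960+0.842)²/(ln 0.6)² gives 121. Freedman (1.960+0.842)²×(1.6/0.4)² gives 126. With the two looks these become 122.7 and 128.1, so 127 is consistent.
- Hazards: placebo −ln(0.6)/8 = 0.0639 per year; OCA 0.6 × 0.0639 = 0.0383.
- Subjects: with uniform accrual, P(event) = 1 − [exp(−6λ) − exp(−10λ)]/(4λ), which averages 0.331 over the arms. Then 127/0.331 ≈ 384, and 384/0.90 ≈ 427, against the stated 428.

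**Formulas for the check.** Let λ₁ be the component hazard and λ₂ the hazard of death without the component, both constant.
- One minus Kaplan-Meier: 1 − exp(−λ₁T)
- Cumulative incidence: λ₁/(λ₁+λ₂) × [1 − exp(−(λ₁+λ₂)T)]
- Greenwood standard error of the Kaplan-Meier estimate: n = 214 per arm, administrative censoring uniform over years 6 to 10, dropout 0.0125 per year (about 10% over 8 years).

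**Assumption.** The protocol gives no cause split. Each hazard is set as a share of the composite hazard, and the shares are varied.

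Worked case, placebo, 8 years, 50%/50%: λ₁ = λ₂ = 0.0319. One minus Kaplan-Meier = 1 − exp(−0.255) = 22.5%. Cumulative incidence = 0.5 × (1 − exp(−0.511)) = 0.5 × 0.40 = 20.0%. The gap is 2.5 points.

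Placebo, 8 years:

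| Component / death share | 1−KM | Cumulative incidence | Gap (points) | Gap in SE |
|---|---|---|---|---|
| 10% / 10% | 5.0% | 4.9% | 0.1 | 0.08 |
| 10% / 30% | 5.0% | 4.6% | 0.4 | 0.22 |
| 20% / 30% | 9.7% | 9.0% | 0.7 | 0.31 |
| 25% / 25% | 12.0% | 11.3% | 0.7 | 0.29 |
| 80% / 20% | 33.5% | 32.0% | 1.5 | 0.43 |
| 70% / 30% | 30.1% | 28.0% | 2.1 | 0.58 |
| 50% / 50% | 22.5% | 20.0% | 2.5 | 0.76 |

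The last three rows give the whole composite hazard to one component plus competing death, so one component carries 50% to 80% of it.

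**OCA arm, 8 years, hazard ratio 0.60 on both hazards.** 50%/50%: 14.2% against 13.2%, 1.0 point, 0.38 SE. 80%/20%: 0.20 SE.

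**Difference between arms.** At 8 years in the 50%/50% case, Kaplan-Meier gives 22.5 − 14.2 = 8.3 points and cumulative incidence 20.0 − 13.2 = 6.8 points. At 10 years with component 50% and death 25%, it is 27.33 − 17.43 = 9.9 against 25.37 − 16.65 = 8.7 points.

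**The case against.** The best case against acting has four parts.

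- **No test changes.** The stratified log-rank and Cox analyses are valid cause-specific comparisons. Among the affected endpoints only MELD of 15 or more is in the testing hierarchy; Section 13.1.10 makes the tests on additional endpoints descriptive and exploratory. This stands. A reader might infer that the gatekeeping on MELD loses error control. It does not, because the log-rank test under cause-specific censoring keeps its level.
- **The effect is small for most components.** With smaller shares the gap is 0.08 to 0.31 SE. Exclusion criterion 5 in Section 8.3 removes conditions that may diminish life expectancy, which argues against the high end for non-liver death. This stands, and it limits the size.
- **Crude counts are also reported.** Sections 13.1.3 and 13.1.8 require the number and percent with events and censored. This helps only in part: crude percentages ignore unequal follow-up and do not correct the curves or medians.
- **The analysis plan could add a competing-risk display.** It could, but the protocol has not left the matter open. It states the censoring rule and names Kaplan-Meier, so an analysis plan that follows it reports the overstated quantity.

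Two further inferences are tempting and fail. One is that Kaplan-Meier mixes differing mortality into the historical-control contrasts. Under the model above, one minus Kaplan-Meier does not contain λ₂; cumulative incidence does. The other is that component curves would add up to the composite if done correctly. Section 7.6 keeps subjects in follow-up after an outcome event, so one subject can contribute to several components, and the curves do not sum under either method.

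**Conclusion.** The point holds for descriptive reporting. For every time-to-event endpoint that excludes all-cause death, the Kaplan-Meier tables and curves overstate the probability of the event whenever subjects die without it. The direction is certain. The size depends on a cause split that the protocol does not give and on constant hazards. At 8 years the placebo excess is about 0.1 to 2.5 points (0.08 to 0.76 SE), and the OCA excess is at most about 1 point (0.38 SE). An excess above half a standard error needs one dominant component in the placebo arm, with competing deaths at about a quarter or more of the composite hazard. If treatment also lowers mortality, the absolute difference between arms is overstated too.

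Nothing confirmatory is affected: the primary endpoint, transplant or all-cause death, the tests, type I error control, the 127 events and the 428 subjects all stand.

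**What to change.** In Sections 13.1.9.1 and 13.1.8, state that for every time-to-event endpoint excluding all-cause death, Aalen-Johansen cumulative incidence will be tabulated and graphed in place of Kaplan-Meier. The competing event is death, or non-liver death where liver-related death is the endpoint or part of it, and also transplant where it precludes the event. Keep the stratified log-rank and Cox analyses for these endpoints and label them cause-specific. Gray's test is optional.

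Keep Kaplan-Meier for the primary composite, for transplant or all-cause death, and for all-cause death.

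The cost is a text change and some programming. No new data are needed, since Section 13.4 already has all deaths adjudicated. The reported component percentages become slightly smaller.

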8.4.1. Other Reasons for Discontinuation of Study or Investigational Product

The following events are considered appropriate reasons for a subject to discontinue investigational product; however, these subjects are expected to continue in the study until study termination (or at the discretion of the Sponsor):

- Subject begins treatment with commercially available OCA
- The Investigator or Sponsor considers that it is advisable or in the best interest of the subject.
- The occurrence of clinical or laboratory AEs considered by the Investigator to be clinically important safety concerns and related to study drug.
- Withdrawal of consent
 - Consent may be fully withdrawn (in which case the subject discontinues both investigational product and study visits and procedures).
 - Consent may be modified to discontinue study visits but allow semi-annual telephone contact.
 - Consent may be modified to discontinue study visits or semi-annual telephone contact but allow continued access to medical records to assess for suspected major adverse cardiovascular events (MACE) and liver-related clinical outcomes.
 - Early termination procedures should be conducted if the subject withdraws consent (See [Section 9.7.15](#)).

The Investigator is encouraged to contact the Sponsor prior to discontinuing a subject from treatment. The Investigator must notify the Sponsor study monitor by telephone or email as soon as possible if any subject prematurely withdraws from the study.

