	Discontinued	Semiannual contact ^c	Telephone contact every 6 months (± 2 weeks)	Combined Visit, Completed as close as possible to last dose IP	
	Discontinued	Record review only ^c	Record review only	Combined visit Completed as close as possible to last dose IP	
Sponsor Termination	Discontinued	N/A	No additional visits except EOT/EOS	Combined visit Completed as close as possible to last dose IP	

Table 8: Early Discontinuation Scenarios (Continued)

	Investigational Product	Consent	Study Visit Status	EOT Visit ^a	EOS Visit ^a
Pregnancy	Interrupted	Retained	Regular Visit Schedule	Complete as close as possible to last dose IP	Complete at Final study visit
	Discontinued	Complete per the above scenarios - Early Termination or Treatment Discontinuation			
Lost to Follow-up	Discontinued	LTF	None	Unable to complete due to LTF status	

EOS = end of study; EOT = end of treatment; IP = investigational product

^a Refer to [Section 7.1.2](#) Schedule of Study Procedures, [Table 2](#) for all procedures and evaluations required at the End of Treatment and End of Study Visits.

^b Includes initiation of commercially available OCA.

^c Outcomes data to be discussed or collected include data related to adjudicated hepatic and cardiovascular event-related data. Additional data such as information on concurrent medical conditions, co-morbidities, relevant adverse events, and concomitant medications may be collected to help facilitate adjudication of these post-study events.

Some assessments noted below may be omitted if they have been completed within the 6 months (or the timeframe otherwise specified) and so long as safety issues do not warrant repeat testing.

Prior to the EOT/EOS Visit:

If possible to do before the visit, when scheduling the EOT/EOS visit, reiterate dosing instructions and advise the subject:

- If applicable, NOT to take investigational product on the morning of the next visit, and
- To bring the investigational product bottle(s); if applicable, s/he will dose at the clinic, and
- To fast overnight (at least 8 hours) prior to the next visit. Fasting is required prior to all study visits, but water is permitted.

During the EOT/EOS Visit:

- Perform a physical examination (including smoking and alcohol consumption habits).
- Review progression to cirrhosis algorithm
- Perform assessments for calculation of Child-Pugh Score.
- Assess and record vital signs (height, weight, temperature, sitting heart rate, respiratory rate, and sitting blood pressure).

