13.1.2. Determination of Sample Size

The target population is subjects who are at higher risk of liver-related clinical complications. Eligible subjects will have a diagnosis of PBC with bilirubin levels $>ULN$ and $\leq 5x ULN$ and/or $ALP > 3 \times ULN$. The following assumptions were used in sample size calculations:

- Exponential survival curves, placebo survival estimate of 0.6 at 8 years with a hazard ratio of 0.60, and total study duration of 10 years (from first subject enrolled), allowing for 4 years of subject accrual and 6 years of follow up.
- Subjects will be randomized in a 1:1 ratio to placebo or OCA.
- The 2 groups will be compared using a 2-sided log rank test at the 5% level of significance.
- Two interim analyses and one final analysis are planned. The first interim analysis will be performed when 50% of the target events are accrued and the second interim will be performed when 75% of the target events are accrued.
- A dropout rate of 10% is assumed

Based on the randomization ratio, significance level, and assumed hazard ratio, a total of 127 events (both groups combined) will provide 80% power to demonstrate a statistically significant difference between OCA and placebo on time to liver-related outcomes, including all-cause mortality.

In addition, based on the remaining assumptions stated above, it is estimated that approximately 428 subjects will be enrolled to attain 127 events.

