13.4. Adjudication Committees

All suspected liver-related clinical outcomes, and MACE/Expanded MACE, that occur after administration of the first dose of investigational product will be reviewed by the following blinded adjudication committees, depending on event type, before inclusion in any analysis. The 2 committees and event types they are responsible for adjudicating are as follows:

- Cardiovascular Adjudication Committee (CAC): Adjudicates all suspected MACE, including all deaths
- Hepatic Outcomes Committee: Adjudicates all deaths and suspected liver-related outcomes

Each adjudication committee will have a charter that documents the reporting of events by the study site, definition of the suspected events to be adjudicated, supply of source documentation

to the committee, entire data flow and process from committee membership, review of the events by the committee, reporting of the final assessment, and the working procedures of the committee.

The adjudication committee members will include experts with relevant adjudication experience; they will not be involved in the study as Investigators, DMC members, or consultants. Any candidate found to have a conflict or whose name is listed on the FDA debarment list is not offered membership. Conflicts of interest are assessed regularly, and if members are found to have a new conflict of interest they will be replaced.

The adjudication of suspected events will be based on available source documentation, including but not limited to individual clinical study data, hospital records, histology, discharge summaries, and/or death certificates. The adjudication committees will not receive any individual subject treatment or site-specific information. The assessment of events will be conducted in compliance with study-specific procedures, manuals, good clinical practice (GCP), and all other applicable regulatory requirements, including the archiving of essential documents.

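### Censoring event-free subjects at last contact, while still counting events found later by record review, makes follow-up depend on the outcome

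*Protocol*

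**What the plan says.** Section 13.1.9.1 fixes the rule for time-to-event endpoints: "subjects who do not experience an event will be censored at the time of their last contact". Last contact is not defined.

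Section 8.4.1 lists levels of reduced consent. The lowest short of full withdrawal is "Consent may be modified to discontinue study visits or semi-annual telephone contact but allow continued access to medical records", for the purpose of finding cardiovascular events and liver-related outcomes. Table 8 (Section 9.7.15) gives these subjects a combined EOT/EOS visit near the last dose and then record review alone. Semi-annual telephone contact has its own row. Footnote c, which applies to both rows, says: "Outcomes data to be discussed or collected include data related to adjudicated hepatic and cardiovascular event-related data".

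Section 13.4 sends to adjudication "All suspected liver-related clinical outcomes, and MACE/Expanded MACE, that occur after administration of the first dose of investigational product", with no end date. Section 13.1.3 says of the primary analysis, in the ITT population: "Only adjudicated events will be included in analyses". No section ends event counting at last contact, and none treats a clean record review as a contact or carries censoring forward to it.

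**The concern.** A subject's time at risk should end on a date that does not depend on whether the event happened. Take two subjects who move to record review at year 2. One has a transplant at year 5, found in the records, and contributes five years and an event. The other is event-free in the records throughout and contributes two years. The analysis keeps the later events of this group and discards the matching event-free time.

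The missing-at-random assumption in Section 13.1.9 does not cover this, because the analysis rule itself creates the dependence. Kaplan-Meier event probabilities come out too high in any arm with such subjects. If the arms differ in how many enter this tier, or when, the hazard ratio and the log-rank test are affected too.

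**Working it through.** **Inputs from Section 13.1.2.** "placebo survival estimate of 0.6 at 8 years with a hazard ratio of 0.60, and total study duration of 10 years"; 4 years' accrual plus 6 years' follow-up; 1:1 allocation; 10% dropout; 127 events for 80% power; about 428 subjects; "2-sided log rank test at the 5% level of significance". Section 13.1.12 places the interim looks at 50% and 75% of events.

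**The plan's own figures reproduce.**
- Events (Freedman): (1.96 + 0.8416)² × (1.6/0.4)² = 7.849 × 16 = 125.6, so 126. Multiplied by 1.0196 for the two O'Brien-Fleming-type looks, this is 128. Schoenfeld gives 121, or 122.7 inflated. Power at 127 events is 79.7% to 81.3%.
- Hazards: −ln(0.6)/8 = 0.0639 per year on placebo; × 0.60 = 0.0383 on OCA.
- Event probability P = 1 − (e^(−6λ) − e^(−10λ))/(4λ): 0.398 and 0.263, mean 0.331.
- Subjects: 127/0.331 = 384; 384/0.9 = 427, against 428 stated.

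The design figures are not in question.

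**Hazard inflation by hand.** Assume 10% of an arm moves to record review at a time uniform over follow-up, and records find every later event. Mean person-time per subject is P/λ. Each event-free switcher loses about half of a mean 8 years, so 4 years.
- Placebo: 0.398/0.0639 = 6.24 years; loss 0.10 × 0.602 × 4 = 0.24; inflation 6.24/6.00 = 1.04.
- OCA: 0.263/0.0383 = 6.87 years; loss 0.10 × 0.737 × 4 = 0.29; inflation 6.87/6.58 = 1.04.

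Simulation gives 3.9% and 4.5%. At 20% it gives 8% to 9%, and at 30%, 13% to 15%. If the switch falls in the first 4 years, the figures for 10%, 20% and 30% are 6–7%, 13–15% and 21–24%.

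**Effect on the hazard ratio** (200,000 subjects per arm, true value 0.60; 0.597 in these runs with no such subjects). Shares and switch times are assumptions.

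| Record-review share, placebo / OCA | Switch over all follow-up | Switch in first 4 years |
|---|---|---|
| 5% / 5% | 0.598 | 0.599 |
| 10% / 10% | 0.599 | 0.600 |
| 20% / 20% | 0.600 | 0.603 |
| 10% / 5% | 0.586 | 0.580 |
| 5% / 10% | 0.611 | 0.619 |
| 20% / 10% | 0.573 | 0.561 |
| 10% / 20% | 0.627 | 0.644 |
| 30% / 10% | 0.547 | 0.522 |
| 10% / 30% | 0.659 | 0.697 |

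With one cut-off for events and event-free time, whether at the end of record coverage or at the last visit, every row returns 0.595 to 0.597.

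**No true effect** (214 per arm, 6,000 runs, single look, switch over all follow-up). Placebo/OCA shares of 10/5, 20/10 and 30/10 give hazard ratios of 0.98, 0.96 and 0.92. Two-sided error is 5.0%, 5.8% and 8.8%, and the part favouring OCA is 3.2%, 4.5% and 8.2% against a nominal 2.5%. Shares of 10/30 give 1.09. A consistent cut-off gives a two-sided 4.7%.

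**Power** (214 per arm, 3,000 runs, switch at 0.25 to 4 years). With 10% of OCA and 5% of placebo, power falls from 85% to 80%. With 15% and 5%, it falls from about 85% to 72–73%. With 15% in both arms it falls by 1 to 2 points. The starting value exceeds 80% because these runs have no dropout: 428 × 0.331 = 142 events.

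**The case against.** **Last contact could be meant to include a record check, and choosing the date is SAP work.** The SAP is not shown and may settle it. But Section 13.1.9.1 states the rule rather than deferring it, and the protocol's usage points the other way: Table 8 separates semi-annual contact from record review, Section 8.4.1 sets telephone contact against record access, and Section 8.4.3 uses contact for contact with the subject.

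**Events found after the EOS visit may not be meant to count.** Footnote c describes them as occurring after study, so a reading in which events and time both stop at EOS is open. This partly stands. However, the events go to adjudication and no section excludes them, so the exclusion, if intended, also has to be written.

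**The shares are unsupported.** This stands. The whole dropout allowance is 10%, subjects who stop product are expected to keep attending, and telephone contact lies between attendance and record review. Scenarios with 15% to 30% of an arm in this one tier exceed that allowance. At 3% of OCA against 1% of placebo the hazard ratio is about 0.61.

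**The direction is unknown.** This stands. A reader might infer that the rule works against OCA because subjects stop it for pruritus and drift to record review. The protocol says that such subjects continue visits. Loss to commercial OCA, which Section 13.1.12 tells the DMC to monitor, could be commoner on placebo and push the other way.

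**MELD ≥15 rests on study laboratory tests, so a clean record does not prove that a subject is free of the composite.** This stands and limits the remedy. Suppose records find only 60% of later composite events (an assumption), with 15% of OCA and 5% of placebo in the tier. The literal rule then gives 0.626. Censoring at the last record review gives 0.58, an error in OCA's favour. Stopping events and time at the last visit gives 0.60.

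**Conclusion.** The concern holds in a limited form. Followed as written, Section 13.1.9.1 together with the record-review tier makes length of follow-up depend on the outcome. The hazard and the Kaplan-Meier event probabilities are then overstated in any arm with such subjects. The hazard ratio is biased only if the tier's share or timing differs between arms, and the sign depends on which arm has more.

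The size rests entirely on assumed shares and switch times and on complete capture of later events: almost nothing with equal shares, 0.01 to 0.02 on the hazard ratio at 10% against 5%, and material only beyond that. It would be tempting to conclude that the trial will lose a specific amount of power, that its type I error is inflated, or that the primary result is biased against OCA. The documents support none of these, since they give neither the size of the tier nor its distribution by arm. The rule still merits correction, because it is wrong in principle and cheap to repair.

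**What to change.** In Section 13.1.9.1, apply one cut-off per endpoint to both events and event-free time: the last date on which the subject's status for that endpoint is known.

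- For death, transplant and other events that records can show, this date includes the date through which medical records were reviewed.
- For the primary composite and MELD ≥15, use the record-review date only where the records are enough to assess every component. Otherwise stop both events and time at the last visit at which all components were assessed, and add a sensitivity analysis that uses the record-review follow-up.
- Record the review date and the date of coverage in the CRF at every review, including those that find nothing.

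The cost is a few sentences in the protocol or SAP and a date entry at each record review. The entry should start early: in a study planned to last about 10 years, dates of reviews that found nothing may be hard to recover afterwards.
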